5.8.3 Use in Pregnancy

If a subject inadvertently becomes pregnant while on treatment with pembrolizumab, the subject will immediately be removed from the study. The site will contact the subject at least monthly and document the subject's status until the pregnancy has been completed or terminated. The outcome of the pregnancy will be reported to the Sponsor and to Merck without delay and within 24 hours to the Sponsor and within 2 working days to Merck if the outcome is a serious adverse experience (e.g., death, abortion, congenital anomaly, or other disabling or life-threatening complication to the mother or newborn).

The study investigator will make every effort to obtain permission to follow the outcome of the pregnancy and report the condition of the fetus or newborn to the Sponsor. If a male subject impregnates his female partner the study personnel at the site must be informed immediately and the pregnancy reported to the Sponsor and to Merck and followed as described above and in Section 7.2.2.

5.8.4 Use in Nursing Women

It is unknown whether pembrolizumab is excreted in human milk. Since many drugs are excreted in human milk, and because of the potential for serious adverse reactions in the nursing infant, subjects who are breast-feeding are not eligible for enrollment.

5.9 Subject Withdrawal/Discontinuation Criteria

Subjects may withdraw consent at any time for any reason or be dropped from the trial at the discretion of the investigator should any untoward effect occur. In addition, a subject may be withdrawn by the investigator or the Sponsor if enrollment into the trial is inappropriate, the trial plan is violated, or for administrative and/or other safety reasons. Specific details regarding discontinuation or withdrawal are provided in Section 7.1.3 – Other Procedures.

A subject must be discontinued from the trial for any of the following reasons:

- The subject or legal representative (such as a parent or legal guardian) withdraws consent.
- Confirmed radiographic disease progression

Note: For unconfirmed radiographic disease progression, please see Section 4.1.5.1

Note: A subject may be granted an exception to continue on treatment with confirmed radiographic progression if clinically stable or clinically improved, please see Section 4.1.5.1

- Unacceptable adverse experiences as described in Section 5.2.1.2
- Intercurrent illness that prevents further administration of treatment

- Investigator's decision to withdraw the subject
- The subject has a confirmed positive serum pregnancy test
- Noncompliance with trial treatment or procedure requirements
- The subject is lost to follow-up
- Completed 24 months of uninterrupted treatment with pembrolizumab or 35 administrations of study medication, whichever is later.

Note: 24 months of study medication is calculated from the date of first dose. Subjects who stop pembrolizumab after 24 months may be eligible for up to one year of additional study treatment if they progress after stopping study treatment provided they meet the requirements detailed in Section 7.1.4.5

- Administrative reasons

The End of Treatment and Follow-up visit procedures are listed in Section 6 (Protocol Flow Chart) and Section 7.1.4 (Visit Requirements). After the end of treatment, each subject will be followed for 30 days for adverse event monitoring (serious adverse events will be collected for 90 days after the end of treatment as described in Section 7.1.5.3.1). Subjects who discontinue for reasons other than progressive disease will have post-treatment follow-up for disease status until disease progression, initiating a non-study cancer treatment, withdrawing consent or becoming lost to follow-up. After documented disease progression each subject will be followed by telephone for overall survival until death, withdrawal of consent, or the end of the study, whichever occurs first.

5.9.1 Discontinuation of Study Therapy after CR

Discontinuation of treatment may be considered for subjects who have attained a confirmed CR that have been treated for at least 24 weeks with pembrolizumab and had at least two treatments with pembrolizumab beyond the date when the initial CR was declared. Subjects who then experience radiographic disease progression no sooner than 8 weeks after completion of pembrolizumab may be eligible for up to one year of additional treatment with pembrolizumab via the Second Course Phase at the discretion of the investigator if no cancer treatment was administered since the last dose of pembrolizumab, the subject meets the safety parameters listed in the Inclusion/Exclusion criteria, and the trial is open. Subjects will resume therapy at the same dose and schedule at the time of initial discontinuation. Additional details are provided in Section 7.1.4.5.

5.9.2. Discontinuation of doxorubicin for patients treated in cohort 1 should be considered after either a cumulative dose of 360 mg/m^2 , a drop in left ventricular ejection fraction below 50%, or 2 cycles after complete remission is confirmed, whichever occurs sooner.

5.10 Subject Replacement Strategy

A subject discontinuing therapy will not be replaced. Patients who are screen-failed but were never treated will be replaced.

5.11 Clinical Criteria for Early Trial Termination

Early trial termination will be the result of the criteria specified below:

1. Quality or quantity of data recording is inaccurate or incomplete
2. Poor adherence to protocol and regulatory requirements
3. Incidence or severity of adverse drug reaction in this or other studies indicates a potential health hazard to subjects
4. Plans to modify or discontinue the development of the study drug

In the event of Merck decision to no longer supply study drug, ample notification will be provided so that appropriate adjustments to subject treatment can be made.

6.0 TRIAL FLOW CHART

6.1 Study Flow Chart

Trial Period:	Screening Phase		Treatment Cycles								End of Treatment	Post-Treatment		
	Pre-screening (Visit 1)	Main Study Screening (Visit 2)	1	2	3	4	To be repeated beyond 8 cycles					Safety Follow-up	Follow Up Visits	Survival Follow-Up
Treatment Cycle/Title:							5	6	7	8				
Scheduling Window (Days):		-28 to -1		± 3	± 3	± 3	± 3	± 3	± 3	± 3	At time of Discont.	30 days post Discont.	Every 8 weeks post Discont.	Every 12 weeks
Administrative Procedures														
Pre-screening Consent	X													
Informed Consent		X												
Inclusion/Exclusion Criteria		X												
Demographics and Medical History		X												
Prior and Concomitant Medication Review		X	X	X	X	X	X	X	X	X		X		
Trial Treatment Administration			X	X	X	X	X	X	X	X				
Post-study anticancer therapy status													X	X
Survival Status														X
Clinical Procedures/Assessments														
Review Adverse Events		X	X	X	X	X	X	X	X	X		X		
Full Physical Examination		X												
Directed Physical Examination			X	X	X	X	X	X	X	X				
Vital Signs and Weight		X	X	X	X	X	X	X	X	X				
ECOG Performance Status		X	X	X	X	X	X	X	X	X				
Laboratory Procedures/Assessments: analysis performed by LOCAL laboratory														
Pregnancy Test – Urine or Serum β-HCG		X												
PT/INR and aPTT		X												
CBC with Differential		X	X	X	X	X	X	X	X	X		X		

Trial Period:	Screening Phase		Treatment Cycles								End of Treatment	Post-Treatment			
	Treatment Cycle/Title:	Pre-screening (Visit 1)	Main Study Screening (Visit 2)	1	2	3	4	To be repeated beyond 8 cycles				Discont.	Safety Follow-up	Follow Up Visits	Survival Follow-Up
Scheduling Window (Days):				-28 to -1	± 3	± 3	± 3	± 3	± 3	± 3	± 3				
Comprehensive Serum Chemistry Panel		X	X	X	X	X	X	X	X	X	X	X	X		
Urinalysis		X		X		X		X		X			X		
T3, FT4 and TSH		X		X		X		X		X			X		
Efficacy Measurements															
Tumor Imaging with CT (chest, abdomen, pelvis, bone scan, other modalities as deemed appropriate clinically)		X			X			X			X				
Cardiac evaluation: Echo, or MUGA and ECG for triple negative and MUGA or ECHO for the HR+ cohort		X								X@					
Tumor Biopsies/Archival Tissue Collection/Correlative Studies Blood															
Archival or Newly Obtained Tissue Collection		X		X#							X				
Correlative Studies Blood Collection##		X		X							X				
#optional ## if pts agree ask for weeks 4,6,8,10, 20,30															
@For triple negative patients, Echo or MUGA evaluations will be repeated after cycle 6, at least a week prior to cycle 7. Subsequent cardiac testing will be carried out as clinically indicated. For hormone receptor positive patients, only a baseline Echo or MUGA scan is required, any subsequent cardiac testing will be as clinically indicated															

7.0 TRIAL PROCEDURES

7.1 Trial Procedures

The Trial Flow Chart - Section 6.0 summarizes the trial procedures to be performed at each visit. Individual trial procedures are described in detail below. It may be necessary to perform these procedures at unscheduled time points if deemed clinically necessary by the investigator.

Furthermore, additional evaluations/testing may be deemed necessary by the Sponsor and/or Merck for reasons related to subject safety. In some cases, such evaluation/testing may be potentially sensitive in nature (e.g., HIV, Hepatitis C, etc.), and thus local regulations may require that additional informed consent be obtained from the subject. In these cases, such evaluations/testing will be performed in accordance with those regulations.

7.1.1 Administrative Procedures

7.1.1.1 Informed Consent

The Investigator must obtain documented consent from each potential subject prior to participating in a clinical trial.

7.1.1.1.1 General Informed Consent

Consent must be documented by the subject's dated signature or by the subject's legally acceptable representative's dated signature on a consent form along with the dated signature of the person conducting the consent discussion.

A copy of the signed and dated consent form should be given to the subject before participation in the trial.

The initial informed consent form, any subsequent revised written informed consent form and any written information provided to the subject must receive the IRB/ERC's approval/favorable opinion in advance of use. The subject or his/her legally acceptable representative should be informed in a timely manner if new information becomes available that may be relevant to the subject's willingness to continue participation in the trial. The communication of this information will be provided and documented via a revised consent form or addendum to the original consent form that captures the subject's dated signature or by the subject's legally acceptable representative's dated signature.

Specifics about a trial and the trial population will be added to the consent form template at the protocol level.

The informed consent will adhere to IRB/ERC requirements, applicable laws and regulations and Sponsor requirements.

7.1.1.2 Inclusion/Exclusion Criteria

All inclusion and exclusion criteria will be reviewed by the investigator or qualified designee to ensure that the subject qualifies for the trial.

7.1.1.3 Medical History

A medical history will be obtained by the investigator or qualified designee. Medical history will include all active conditions, and any condition diagnosed within the prior 10 years that are considered to be clinically significant by the Investigator. Details regarding the disease for which the subject has enrolled in this study will be recorded separately and not listed as medical history.

7.1.1.4 Prior and Concomitant Medications Review

7.1.1.4.1 Prior Medications

The investigator or qualified designee will review prior medication use, including any protocol-specified washout requirement, and record prior medication taken by the subject within 28 days before starting the trial. Treatment for the disease for which the subject has enrolled in this study will be recorded separately and not listed as a prior medication.

7.1.1.4.2 Concomitant Medications

The investigator or qualified designee will record medication, if any, taken by the subject during the trial. All medications related to reportable SAEs and ECIs should be recorded as defined in Section 7.2.

7.1.1.5 Disease Details and Treatments

7.1.1.5.1 Disease Details

The investigator or qualified designee will obtain prior and current details regarding disease status.

7.1.1.5.2 Prior Treatment Details

The investigator or qualified designee will review all prior cancer treatments including systemic treatments, radiation and surgeries.

7.1.1.5.3 Subsequent Anti-Cancer Therapy Status

The investigator or qualified designee will review all new anti-neoplastic therapy initiated after the last dose of trial treatment. If a subject initiates a new anti-cancer therapy within 30 days after the last dose of trial treatment, the 30 day Safety Follow-up visit must occur before

the first dose of the new therapy. Once new anti-cancer therapy has been initiated the subject will move into survival follow-up.

7.1.1.6 Assignment of Screening Number

All consented subjects will be given a unique screening number according to their designated cohorts (Cohort 1: triple negative; Cohort 2 HR+).

7.1.1.7 Assignment of Cohort Number will be based as above.

7.1.1.8 Trial Compliance (Medication/Diet/Activity/Other)

Interruptions from protocol-specified treatment for greater than 12 weeks require consultations between the investigator/PI and sponsors.

Instructions on how to prepare pembrolizumab will be per Pharmacy manual. Doxorubicin and AIs will be prepared or prescribed as per approved product label and standard practice guidelines.

7.1.2 Clinical Procedures/Assessments

7.1.2.1 Adverse Event (AE) Monitoring

The investigator or qualified designee will assess each subject to evaluate for potential new or worsening AEs as specified in the Trial Flow Chart and more frequently if clinically indicated. Adverse experiences will be graded and recorded throughout the study and during the follow-up period according to NCI CTCAE Version 4.0 (see Section 11.2). Toxicities will be characterized in terms regarding seriousness, causality, toxicity grading, and action taken with regard to trial treatment.

For subjects receiving treatment with pembrolizumab all AEs of unknown etiology associated with pembrolizumab exposure should be evaluated to determine if it is possibly an event of clinical interest (ECI) of a potentially immunologic etiology (termed immune-related adverse events, or irAEs); see the separate ECI guidance document in Appendix 4 regarding the identification, evaluation and management of potential irAEs.

Please refer to section 7.2 for detailed information regarding the assessment and recording of AEs.

7.1.2.2 Full Physical Exam

The investigator or qualified designee will perform a complete physical exam during the screening period. Clinically significant abnormal findings should be recorded as medical history. A full physical exam should be performed during screening,

7.1.2.3 Directed Physical Exam

For cycles that do not require a full physical exam per the Trial Flow Chart, the investigator or qualified designee will perform a directed physical exam as clinically indicated prior to trial treatment administration.

7.1.2.4 Vital Signs

The investigator or qualified designee will take vital signs at screening, prior to the administration of each dose of trial treatment and at treatment discontinuation as specified in the Trial Flow Chart (Section 6.0). Vital signs should include temperature, pulse, respiratory rate, weight and blood pressure. Height will be measured at screening only.

7.1.2.5 Eastern Cooperative Oncology Group (ECOG) Performance Scale

The investigator or qualified designee will assess ECOG status (see Section 11.1) at screening, prior to the administration of each dose of trial treatment and discontinuation of trial treatment as specified in the Trial Flow Chart.

7.1.2.6 Tumor Imaging and Assessment of Disease

Tumor imaging may be performed by CT, MRI, FDG/PET/CT but the same technique needs to be performed throughout the trial. Cardiac assessment (Cohort 1 patients) can be performed by MUGA or Echocardiogram.

7.1.2.7 Tumor Tissue Collection and Correlative Studies Blood Sampling

Laboratory Procedures/Assessments

Details regarding specific laboratory procedures/assessments to be performed in this trial are provided below Laboratory Safety Evaluations (Hematology, Chemistry and Urinalysis)

Laboratory tests for hematology, chemistry, urinalysis, and others are specified in Table 5.

Table 5 Laboratory Tests

Hematology	Chemistry	Urinalysis	Other
Hematocrit	Albumin	Blood	Serum β -human chorionic gonadotropin†
Hemoglobin	Alkaline phosphatase	Glucose	(β -hCG)†
Platelet count	Alanine aminotransferase (ALT)	Protein	PT (INR)
WBC (total and differential)	Aspartate aminotransferase (AST)	Specific gravity	aPTT
Red Blood Cell Count	Lactate dehydrogenase (LDH)	Microscopic exam (If abnormal)	Total triiodothyronine (T3)
Absolute Neutrophil Count	Carbon Dioxide ‡	results are noted	Free tyroxine (T4)
Absolute Lymphocyte Count	(CO_2 or bicarbonate)	Urine pregnancy test †	Thyroid stimulating hormone (TSH)
	Uric Acid		PK
	Calcium		
	Chloride		Blood for correlative studies
	Glucose		
	Phosphorus		
	Potassium		
	Sodium		
	Magnesium		
	Total Bilirubin		
	Direct Bilirubin		
	Total protein		
	Blood Urea Nitrogen		

† Perform on women of childbearing potential only. If urine pregnancy results cannot be confirmed as negative, a serum pregnancy test will be required.

‡ If considered standard of care in your region.

Laboratory tests for screening or entry into the Second Course Phase should be performed within 7 days prior to the first dose of treatment. After Cycle 1, pre-dose laboratory procedures can be conducted up to 72 hours prior to dosing. Results must be reviewed by the investigator or qualified designee and found to be acceptable prior to each dose of trial treatment.

7.1.2.8 Pharmacokinetic/Pharmacodynamic Evaluations

Not applicable.

7.1.2.8.1 Blood Collection for Serum Pembrolizumab

N/A

7.1.2.8.2 Blood Collection for Anti-Pembrolizumab Antibodies NA

7.1.3 Other Procedures

7.1.3.1 Withdrawal/Discontinuation

When a subject discontinues/withdraws prior to trial completion, all applicable activities scheduled for the final trial visit should be performed at the time of discontinuation. Any adverse events which are present at the time of discontinuation/withdrawal should be followed in accordance with the safety requirements outlined in Section 7.2 - Assessing and Recording Adverse Events. Subjects who a) attain a CR or b) complete 24 months of treatment with pembrolizumab may discontinue treatment with the option of restarting treatment if they meet the criteria specified in Section 7.1.4.5. After discontinuing treatment following assessment of CR, these subjects should return to the site for a Safety Follow-up Visit (described in Section 7.1.5.3.1) and then proceed to the Follow-Up Period of the study (described in Section 7.1.5.4).

7.1.3.2 Blinding/Unblinding

Not applicable.

7.1.4 Visit Requirements

Visit requirements are outlined in Section 6.0 - Trial Flow Chart. Specific procedure-related details are provided above in Section 7.1 - Trial Procedures.

7.1.4.1 Screening

Patients will be identified by the breast cancer team at their regular weekly treatment planning conference, or as they are being seen by team members.

7.1.4.1.1 Screening Period

Laboratory information should be within 7 days of initiating treatment, radiographic and other images should be within 28 days prior to starting treatment.

7.1.4.2 Treatment Period

See 6.1.

7.1.4.3 Post-Treatment Visits

See section 6.1

7.1.5.3.1 Safety Follow-Up Visit

The mandatory Safety Follow-Up Visit should be conducted approximately 30 days after the last dose of trial treatment or before the initiation of a new anti-cancer treatment, whichever comes first. All AEs that occur prior to the Safety Follow-Up Visit should be recorded. Subjects with an AE of Grade > 1 will be followed until the resolution of the AE to Grade 0-1 or until the beginning of a new anti-neoplastic therapy, whichever occurs first. SAEs that occur within 90 days of the end of treatment or before initiation of a new anti-cancer treatment should also be followed and recorded. Subjects who are eligible for retreatment with pembrolizumab (as described in Section 7.1.4.5) may have up to two safety follow-up visits, one after the Treatment Period and one after the Second Course Phase.

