Duration of Participation	
After signing the informed consent form (ICF), passing the screening phase and initiating therapy, patients will participate until death or discontinuation from trial treatment due to progression. Patients discontinuing treatment for reasons other than progression will be followed until progression and treatment-related toxicities have resolved or another treatment regimen is initiated. Treatment with pembrolizumab for patients of the triple negative cohort (treated with 6 cycles of doxorubicin/pembrolizumab) will continue with pembrolizumab until disease progression, treatment-related unacceptable toxicities, intercurrent illness preventing further administration of study drug, subject or investigator's decision to withdraw, pregnancy, or, if a patient receives a total of 24 months of pembrolizumab (including the cycles given with doxorubicin). Patients in the hormone-receptor positive cohort may also receive up to 24 months of pembrolizumab, as well. They can continue on their selected anti-estrogen therapy (whichever aromatase inhibitor was chosen with pembrolizumab) until progression. Patients achieving a confirmed complete response may consider stopping pembrolizumab within a year of such response, and could be retreated within 12 months from stoppage. Subjects who stop pembrolizumab with stable disease or better may be eligible for up to one year of additional pembrolizumab therapy if they progress no sooner than 8 weeks after stopping study treatment, for either cohort.
 
After the end of treatment patients will be followed for 30 days for adverse event (AE) monitoring and serious adverse events (SAEs) and events of clinical interest will be collected for 90 days after the end of treatment, or 30 days after the end of treatment if a patient initiates new anti-cancer therapy or until the treatment toxicities clearly stabilize or resolve (whichever is first).

[figure not shown]

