5.3.1.2 Dose Modification

Adverse events (both non-serious and serious) associated with pembrolizumab exposure may represent an immunologic etiology. These adverse events may occur shortly after the first dose or several months after the last dose of treatment. Pembrolizumab must be withheld for drug-related toxicities and severe or life-threatening AEs as per Table 3 below. See Section 5.6.1 and Events of Clinical Interest Guidance Document for supportive care guidelines, including use of corticosteroids. Table 3

Dose Modification Guidelines for Drug-Related Adverse Events

Toxicity	Hold Treatment For Grade	Timing for Restarting Treatment	Discontinue Subject
Diarrhea/Colitis	2-3	Toxicity resolves to Grade 0-1.	Toxicity does not resolve within 12 weeks of last dose or inability to reduce corticosteroid to 10 mg or less of prednisone or equivalent per day within 12 weeks.
	4	Permanently discontinue	Permanently discontinue
AST, ALT, or Increased Bilirubin	2	Toxicity resolves to Grade 0-1	Toxicity does not resolve within 12 weeks of last dose.
	3-4	Permanently discontinue (see exception below) ¹	Permanently discontinue
Type 1 diabetes mellitus (if new onset) or Hyperglycemia	T1DM or 3-4	Hold pembrolizumab for new onset Type 1 diabetes mellitus or Grade 3-4 hyperglycemia associated with evidence of beta cell failure.	Resume pembrolizumab when patients are clinically and metabolically stable.
Hypophysitis	2-3	Toxicity resolves to Grade 0-1	Toxicity does not resolve within 12 weeks of last dose or inability to reduce corticosteroid to 10 mg or less of prednisone or equivalent per day within 12 weeks.
	4	Permanently discontinue	Permanently discontinue
Hyperthyroidism	3	Toxicity resolves to Grade 0-1	Toxicity does not resolve within 12 weeks of last dose or inability to reduce corticosteroid to 10 mg or less of prednisone or equivalent per day within 12 weeks.
	4	Permanently discontinue	Permanently discontinue
Hypothyroidism	2-4	Therapy with pembrolizumab can be continued while treatment for the thyroid disorder is instituted	Therapy with pembrolizumab can be continued while treatment for the thyroid disorder is instituted.
Infusion Reaction	3-4	Permanently discontinue	Permanently discontinue
Pneumonitis	2	Toxicity resolves to Grade 0-1	Toxicity does not resolve within 12 weeks of last dose or inability to reduce corticosteroid to 10 mg or less of prednisone or equivalent per day within 12 weeks.
	3-4	Permanently discontinue	Permanently discontinue

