7.1.4.4.1 Survival Follow-up

Once a subject experiences confirmed disease progression or starts a new anti-cancer therapy, the subject moves into the survival follow-up phase and should be contacted by telephone every 12 weeks to assess for survival status until death, withdrawal of consent, or the end of the study, whichever occurs first.

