7.2.13 Immediate Reporting of Adverse Events to Merck

7.2.13.1 Serious Adverse Events

A serious adverse event is any adverse event occurring at any dose or during any use of Merck's product that:

- Results in death;
- Is life threatening;
- Results in persistent or significant disability/incapacity;
- Results in or prolongs an existing inpatient hospitalization;
- Is a congenital anomaly/birth defect;
- Is a new cancer (that is not a condition of the study);
- Is associated with an overdose;
- Is an other important medical event

Refer to Table 6 for additional details regarding each of the above criteria.

Progression of the cancer under study is not considered an adverse event unless it results in hospitalization or death.

Any serious adverse event, or follow up to a serious adverse event, including death due to any cause other than progression of the cancer under study that occurs to any subject from the time the consent is signed through 90 days following cessation of treatment, or the initiation of new anti-cancer therapy, whichever is earlier, whether or not related to Merck product, must be reported within 24 hours to the Sponsor and within 2 working days to Merck Global Safety.

Non-serious Events of Clinical Interest will be forwarded to Merck Global Safety and will be handled in the same manner as SAEs.

Additionally, any serious adverse event, considered by an investigator who is a qualified physician to be related to Merck product that is brought to the attention of the investigator at any time outside of the time period specified in the previous paragraph also must be reported immediately to the Sponsor and to Merck.

SAE reports and any other relevant safety information are to be forwarded to the Merck Global Safety [contact]

A copy of all 15 Day Reports and Annual Progress Reports is submitted as required by FDA, European Union (EU), Pharmaceutical and Medical Devices agency (PMDA) or other local regulators. Investigators will cross reference this submission according to local regulations to the Merck Investigational Compound Number (IND, CSA, etc.) at the time of submission. Additionally investigators will submit a copy of these reports to Merck & Co., Inc. (Attn: Worldwide Product Safety; [contact]) at the time of submission to FDA.

All subjects with serious adverse events must be followed up for outcome.

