7.2.13.2 Events of Clinical Interest

Selected non-serious and serious adverse events are also known as Events of Clinical Interest (ECI) and must be recorded as such on the Adverse Event case report forms/worksheets and reported within 24 hours to the Sponsor and within 2 working days to Merck Global Safety. (Attn: Worldwide Product Safety; [contact])Events of clinical interest for this trial include:

1. an overdose of Merck product, as defined in Section 7.2.1 - Definition of an Overdose for This Protocol and Reporting of Overdose to the Sponsor, that is not associated with clinical symptoms or abnormal laboratory results.
2. an elevated AST or ALT lab value that is greater than or equal to 3X the upper limit of normal and an elevated total bilirubin lab value that is greater than or equal to 2X the upper limit of normal and, at the same time, an alkaline phosphatase lab value that is less than 2X the upper limit of normal, as determined by way of protocol-specified laboratory testing or unscheduled laboratory testing.*

***Note:** These criteria are based upon available regulatory guidance documents. The purpose of the criteria is to specify a threshold of abnormal hepatic tests that may require

an additional evaluation for an underlying etiology. The trial site guidance for assessment and follow up of these criteria can be found in the Investigator Trial File Binder (or equivalent).

1. Additional adverse events:

A separate guidance document has been provided entitled “Event of Clinical Interest Guidance Document” (previously entitled, “Event of Clinical Interest and Immune-Related Adverse Event Guidance Document”). This document can be found in Appendix 4 and provides guidance regarding identification, evaluation and management of ECIs and irAEs.

ECIs (both non-serious and serious adverse events) identified in this guidance document from the date of first dose through 90 days following cessation of treatment, or 30 days after the initiation of a new anticancer therapy, whichever is earlier, need to be reported within 24 hours to the Sponsor and within 2 working days to Merck Global Safety. (Attn: Worldwide Product Safety; [contact]), regardless of attribution to study treatment, consistent with standard SAE reporting guidelines.

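### SAEs and ECIs must be captured to day 90 after treatment, but no adverse-event query is scheduled after day 30, so late immune events may be under-counted

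*Combined protocol and SAP*

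**What the plan says.** **The duty runs to day 90.**

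- Section 1.0 (Duration of Participation): SAEs and "events of clinical interest will be collected for 90 days after the end of treatment", with a shorter limit if new therapy starts.
- Section 5.9: SAEs are collected for 90 days.
- Section 7.1.5.3.1: "SAEs that occur within 90 days of the end of treatment or before initiation of a new anti-cancer treatment should also be followed and recorded".
- Section 7.2.13.1: SAEs are reportable "from the time the consent is signed through 90 days following cessation of treatment", or until new anti-cancer therapy if that is earlier.
- Section 7.2.13.2: ECIs, serious or not and whatever their attribution, are reportable "from the date of first dose through 90 days following cessation of treatment, or 30 days after the initiation of a new anticancer therapy"; the first limit reached applies.

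**The scheduled assessment stops at day 30.** In section 6.1 the row "Review Adverse Events" is marked at screening, at each cycle and at the Safety Follow-up, headed "30 days post Discont". It is blank for Follow Up Visits and Survival Follow-Up. Those two columns carry post-study therapy status, and the survival column also carries survival status.

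**The text adds contacts but no safety question.** Section 7.1.4.4 has patients who stopped without progression imaged every 6 weeks to follow their disease. Under section 7.1.4.4.1, patients with confirmed progression or new therapy "should be contacted by telephone every 12 weeks to assess for survival status".

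**Late onset is expected.** Of adverse events that may be immunologic, section 5.3.1.2 says: "These adverse events may occur shortly after the first dose or several months after the last dose of treatment".

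**The concern.** A reporting duty tells a site what to do once it knows of an event. It does not create an occasion on which someone asks. If a site follows the schedule as written, nobody is due to ask about SAEs or ECIs between the Safety Follow-up and day 90, and what is recorded depends on the patient, or another clinician, bringing it forward. Non-serious ECIs are the most exposed, because they are less likely to be volunteered than an event that leads to hospital admission.

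Toxicity is a secondary objective in both cohorts (section 3.2), and section 4.1.5 has immune-related events collected and designated as ECIs. In cohorts this small each event counts: one patient is 1/36 = 2.8 percentage points in Cohort 1 and 1/20 = 5 points in Cohort 2.

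**Working it through.** The plan gives no figure for late events or for their capture, so there is nothing to reproduce. The check sets the windows against the scheduled contacts.

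**1. Is the flow chart the governing schedule?** Section 7.1.2.1 ties adverse-event assessment to the flow chart, with more frequent assessment where clinically needed. Section 7.1.4 refers visit requirements to it, and section 7.1.4.3 (post-treatment visits) only points to section 6.1. The routine ECI check in section 7.2.13.2 takes place before each dose, so it ends with treatment.

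**2. Length of the unscheduled stretch, window fully open.** 90 − 30 = 60 days; 60/90 = 67%.

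**3. Contacts inside days 31 to 90** (nominal days from discontinuation; the documents do not state when the 12-week clock for survival calls starts, so counting from discontinuation is an assumption):

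| Contact | Inside the window | Next one | Days to day 90 after the last contact |
|---|---|---|---|
| Follow-up visit, flow chart, 8 weeks | day 56 | day 112 | 90 − 56 = 34 |
| Imaging visit, section 7.1.4.4, 6 weeks | days 42 and 84 | day 126 | 90 − 84 = 6 |
| Survival call, 12 weeks | day 84 | day 168 | 90 − 84 = 6 |

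None has an SAE or ECI query, and none is set at or just after day 90. Adding a query to these contacts alone would still leave between 6 and 34 days uncovered. A symmetric day 90 ± 7 contact could fall on day 83 and miss the last 7 days.

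**4. Effect of new anti-cancer therapy.** Let it start on day t.

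- SAE gap under sections 7.1.5.3.1 and 7.2.13.1: t − 30 if t is after day 30. It is nil if t is earlier, because section 7.1.1.5.3 brings the Safety Follow-up forward to before the new therapy.
- ECI gap under section 7.2.13.2: from the Safety Follow-up to the earlier of day 90 and day t + 30.
- Section 1.0 instead ends both at day 30 if new therapy starts, or at stabilization or resolution of toxicities if that comes first.

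| t | SAE gap | ECI gap (7.2.13.2) | Gap under section 1.0 |
|---|---|---|---|
| 20 (Safety Follow-up on day 20) | 0 | 50 − 20 = 30 days | at most 10 days (day 20 to 30) |
| 35 | 35 − 30 = 5 days | 65 − 30 = 35 days | 0 |
| 60 | 60 − 30 = 30 days | 90 − 30 = 60 days | 0 |

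The 60 days are thus a maximum, and the gap for a given patient depends on which rule is applied.

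**5. Illustration of scale, on assumed rates only.** Take 36 + 20 = 56 patients, all with an open window, and an assumed proportion with an SAE or ECI in days 31 to 90. Expected number = 56 × rate; unreported = 25% to 50% of that, also assumed.

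| Assumed rate | Expected | Unreported at 25% to 50% |
|---|---|---|
| 2% | 1.1 | 0.3 to 0.6 |
| 5% | 2.8 | 0.7 to 1.4 |
| 10% | 5.6 | 1.4 to 2.8 |

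**The case against.** The strongest reply is that capture to day 90 is already mandatory. SAEs and ECIs go to the sponsor within 24 hours. Section 7.1.5.3.1 has adverse events above Grade 1 followed until they settle or new therapy starts. Section 7.1.2.1 has events recorded through follow-up and allows extra assessments. Section 5.6.1 keeps recording concomitant medication for SAEs and ECIs after day 30. Section 7.2.13.1 accepts related SAEs that come to light outside the window. Patients who stopped without progression are also seen for imaging, where an event could surface. Finally, the ECI guidance document is not reproduced in the text available here, and it may prescribe post-treatment contact.

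Much of this stands. It rules out a stronger reading that is tempting, namely that late events are under-counted. The documents give neither a late-event rate nor a capture rate, so only a risk is shown. Nor does the 67% measure lost events: it is a share of calendar days, and it shrinks when new therapy starts. A reader might also infer that patients who progressed are the worst affected and the majority. The documents do not say how often progression ends treatment, and those patients may start new therapy early, which closes the SAE window.

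What the reply does not supply is a scheduled question. Each route it cites acts on an event already known, or leaves the asking to discretion.

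**Conclusion.** The mismatch is real. The text requires SAE and ECI capture to day 90, the last scheduled adverse-event review is at day 30, and no later contact is assigned an SAE or ECI query. For a patient whose window stays open, up to 60 of 90 days rest on unscheduled reporting, and late immune events may be under-counted by an unknown amount.

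The consequence is limited to the description of late toxicity, a secondary objective. Neither cohort's response-rate decision rule nor the first-cycle DLT rules depend on it. The point is worth correcting because the plan itself expects late immune events and the remedy is cheap.

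The conclusion rests on reading the flow chart as the operative schedule, as sections 7.1.2.1 and 7.1.4 direct, and on the assumption that the ECI guidance document adds no post-treatment contact. Two inconsistencies make the window harder to apply: the rule for shortening it differs between sections 1.0, 7.1.5.3.1, 7.2.13.1 and 7.2.13.2, and the follow-up interval is 8 weeks in section 6.1 but 6 weeks in section 7.1.4.4.

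**What to change.** - **Section 6.1:** mark the adverse-event review row, limited to SAEs and ECIs, at every Follow-Up Visit and survival call that falls within the 90-day window.
- **Sections 7.1.5.3.1 and 7.1.4.4.1:** state that every patient whose window is still open, whether in follow-up or in survival follow-up, is asked about SAEs and ECIs since the Safety Follow-up at one contact on or shortly after day 90. Day 90 to 97 would serve, by telephone or at an existing contact moved to that time. Starting the range at day 90 keeps the last days of the window covered.
- **Sections 1.0, 7.1.5.3.1, 7.2.13.1 and 7.2.13.2:** reconcile how new anti-cancer therapy ends the SAE and ECI windows, so that sites know whose window is open.
- **Sections 6.1 and 7.1.4.4:** reconcile the follow-up interval.

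The cost is a few minutes per contact, possibly one extra or re-timed call for some patients, and possibly slightly more reported late events. The sample size and decision rules do not change.
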